All participants who are women of child bearing potential will receive a urine pregnancy dip test at screening and prior to any CT scan and surgical procedure. Educate the subject that during participation in this clinical trial they are not to become pregnant and that pregnancy will result in their removal from the clinical trial.

5.4.3 Describe the measures to prevent pregnancy, and their required duration of use, that will be discussed with women of child-bearing potential during and following exposure to research procedures:

All participants who are women of child bearing potential will receive a urine pregnancy dip test at screening and prior to any CT scan and surgical procedure. Educate the subject that during participation in this clinical trial they are not to become pregnant and that pregnancy will result in their removal from the clinical trial.

View: 5.05

Section 5 - Potential Risks and Benefits of Study Participation

5.5 Do any of the research procedures pose a potential risk of causing genetic mutations that could lead to birth defects?* Possibly or Definitely

5.5.1 List the research procedures that pose a potential risk of genetic mutations/birth defects:

CT Scans and Anesthesia used for Fat grafting procedure

5.5.2 Describe the measures to prevent pregnancy, and their required duration of use, in female subjects and female partners of male subjects during and following exposure to research procedures:

All participants who are women of child bearing potential will receive a urine pregnancy dip test at screening and prior to any CT scan and surgical procedure. Educate the subject that during participation in this clinical trial they are not to become pregnant and that pregnancy will result in their removal from the clinical trial.

View: 5.06 - 5.06(a)

Section 5 - Potential Risks and Benefits of Study Participation

5.6 Are there any alternative procedures or courses of treatment which may be of benefit to the subject if they choose not to participate in this study?* Yes - Describe below:

If Yes, describe in detail:- Receive fat grafting procedure as standard of care- Receive another plastic surgery procedure to address their injury and/or appearance.

View: 5.07 - 5.07(a)

Section 5 - Potential Risks and Benefits of Study Participation

5.7 Describe the specific endpoints (e.g., adverse reactions/events, failure to demonstrate effectiveness, disease progression) or other circumstances (e.g., subject's failure to follow study procedures) that will result in discontinuing a subject's participation?* Describe below:

Noncompliance of study visits (including but not limited to completion of screening and study visit procedures). Development of complications that obscures evaluation of the fat graft results, i.e. severe infection at the graft site resulting in a need for further surgery.

View: 5.08 -5.08(a)

Section 5 - Potential Risks and Benefits of Study Participation

5.8 Will any individuals other than the investigators/research staff involved in the conduct of this research study and authorized representatives of the University Research Conduct and Compliance Office (RCCO) be permitted access to research data/documents (including medical record information) associated with the conduct of this research study?* Yes

5.8.1 Identify the 'external' persons or entity who may have access to research data/documents and the purpose of this access:

Department of Defense and their contracted entities will review and/or obtain identifiable information; which may include the subject's identifiable medical information related to participation in this research study for the purpose of monitoring the accuracy and completeness of the research data and for preparing required scientific analyses of the research data. Authorized representatives of the UPMC hospitals or other affiliated health care providers may have access to identifiable information (which may include the subject's identifiable medical information) related to their participation in this research study for the purpose of (1) fulfilling orders, made by investigators, for hospital and health care services (e.g. laboratory tests) associated with this research study participation, (2) addressing correct payment for tests and procedures ordered by the investigators, and/or (3) for internal hospital operations (i.e. quality assurance). This research study will result in identifiable information that will be placed into the subject's medical records held at UPMC. The nature of the identifiable information resulting from the subject's participation in this research study that will be recorded in their medical record will be derived from the medical/surgical (fat grafting procedure). Psychiatric interview information will be entered into the medical record only if it is important to ensure the subject's medical/physical safety. In unusual cases, the investigators may be required to release identifiable information (which may include your identifiable medical information) related to your participation in this research study in response to an order from a court of law. If the investigators learn that you or someone with whom you are involved is in serious danger or potential harm, they will need to inform, as required by Pennsylvania law, the appropriate agencies.

5.8.2 Will these 'external' persons or entity have access to identifiable research data/documents?

*Yes - Describe below:

If **Yes**, describe how they will protect the confidentiality of the research data: While the study funding source, Department of Defense (DOD), understands the importance of maintaining the confidentiality of the identifiable research and medical information, the UPMC and the University of Pittsburgh cannot guarantee the confidentiality of this information after it has been obtained by the Department of Defense.

5.9 Has or will a Federal Certificate of Confidentiality be obtained for this research study?

* No

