- 1.2 **Specific Aims: List the goals of the proposed study (e.g., describe the relevant hypotheses or the specific problems or issues that will be addressed by the study).**Facial trauma injuries, especially those sustained in military combat and severe automobile crashes, are characterized by destruction of bone and soft tissue anatomy. While the bony skeleton can often be reconstructed, the overlying soft tissue is difficult to restore. Similar deformities typically seen after treatment of facial trauma. Importantly, it is the structure of the soft tissue that imparts the normal human form, and adequate reconstruction of soft tissue defects allows trauma victims to reintegrate into society. Accepted procedures for soft tissue reconstruction of the face involve tissue flap reconstruction procedures and autologous fat grafting. Tissue flap operations are extensive, often including microvascular surgery, and do not precisely correct the deformities. Fat grafting is a less invasive technique that allows for more precise shaping of the reconstructed tissues. However, autologous fat grafts may undergo resorption that can affect the appearance of the reconstruction over time. The degree of change in appearance after fat grafting has not been well studied for facial trauma patients. We hypothesize that initial results from fat grafting for facial trauma will show good restoration of tissue volume, and that a majority of the fat tissue will remain in place over time. Additionally, we hypothesize that the cellular properties of the fat precursor cells (preadipocytes) may correlate with fat graft retention. The specific aims of the study are: 1) Assess facial appearance and soft tissue volume before and after autologous fat grafting using CT scans, standard photography and 3D photography. 2) Assess cellular properties of the cells within the fat graft 3) Measure of quality of life in patients before and after autologous fat grafting using validated psychosocial measures. 4) Compare the cotton rolling to centrifugation method of autologous fat grafting. This will be accomplished by analyzing outcomes of facial appearance and soft tissue volume in subjects in this study compared to those subjects enrolled in protocol PRO09060101.

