has been accrued in the craniofacial region. Indications include post-traumatic reconstruction, congenital deformities, post-surgical deformities (e.g. cancer resection), facial atrophy associated with HIV treatment, acne scars, and cosmetic correction of facial aging (2-25). Adipose tissue is injected into the subcutaneous planes and into deep fat pads. Volumes of adipose tissue injection in the facial region tend to range from several ml to over 100 ml. Procedures are often performed in a single stage, but staged fat injections are not uncommon. Advantages of autologous fat grafting for craniofacial reconstruction Autologous fat grafting has many advantages for craniofacial reconstruction compared with alternative treatments. Other standard methods of restoring soft tissue volume involve the surgical transfer of tissue flaps, either on a vascular pedicle or by microvascular technique. These flap procedures are much more invasive, carry a risk of donor site morbidity, and do not allow for precise. We have had significant and successful improvement in all subjects, with retention of volume in the range of 65%. Our basic science team recently published a paper in Plastic and Reconstructive Surgery Journal demonstrating in an animal model that a manual processing technique for separating the aqueous layer from the fat graft material without centrifugation provides superior volume retention after healing. This manual separation method requires less equipment in the operating room, making it more applicable for a variety of clinical settings in the military health system. Craniofacial Injuries Have Serious Psychosocial Sequele and Affect Quality of Life Many individuals who suffer significant facial disfigurement from injury experience psychological distress and impairment in functioning not limited to the acute phase of injury but over a longer term period of treatment, recovery and adjustment (26, 27). Symptoms of anxiety and depression and post-traumatic stress disorder are common—both before and after surgery (28, 29). In their study of individuals with severe facial lacerations and disfigurement, Levine and colleagues (30) noted the “powerful [influence] of facial appearance and body image on the quality of life” of these individuals. Clinical studies of facial trauma victims, using structured interview and self-report instruments, also document the common experience of social anxiety and social withdrawal—problems that can significantly compromise social and occupational functioning and engagement in social and leisure time activities—ultimately impacting the overall quality of life (31, 32). Facial burn victims report that interactions with strangers and with children and adolescents can be particularly discomfiting in response to visible non-verbal communications of negative affect (e.g. surprise, disgust) (27). Results of outcome studies of burn patients suggest that personal adjustment and quality of life are better predicted by psychosocial factors than site of injury (33). Pre- and post-surgical psychosocial factors such as social support, coping skills, and satisfaction with surgical outcomes are significant predictors of personal and social adjustment and quality of life outcomes, in addition to the physical outcomes of surgical intervention for disfigurement (34-36). Significant is the fact that there are few studies of the psychosocial impact of complex CMF battle injuries and post-surgical changes in psychosocial well-being and quality of life.

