Serial computed tomography imaging will be performed to assess the total soft tissue volume before fat grafting and afterwards at three time points: immediately post-grafting, three months post-graft and nine month post-graft. Comparisons of the post-graft tissue volume to pre-treatment volume will be performed using a paired t-test model. Repeated measures analysis of variance will be used to evaluate change over time in all outcome measures. Using standard conventions of $\alpha=0.05$ and $\beta=0.8$, an enrollment of ten patients will provide sufficient power to detect a clinically meaningful differences in the volume of soft tissue between groups.. Based on published effect sizes for clinically significant medical outcomes on the SF-36 (i.e., 0.5 to 0.7), e.g., following surgery for dentofacial deformities ($d = 0.6$) (64), and medium (0.5 – 0.79) to large (0.8 to > 3.0) effect sizes on SF-36 social functioning outcomes of neck surgery (65) and orthopedic surgery (66), it is expected that a sample of 10 patients will provide sufficient power to detect a medium effect size ($d = 0.5$) on SF-36 measures of social functioning and quality of life, applying standard conventions of $\alpha = 0.05$ and $\beta = 0.8$. The cotton rolling fat processing technique takes place in the Operative Room during the study surgery directly following the collection of the lipoaspirate. Outcome of facial appearance and soft tissue volume in subjects who were injected with fat grating material processed by the cotton rolling technique in this protocol will be compared to those subjects in protocol PRO09060101 who were injected with fat grafting material using the centrifuged technique. Significance level (adjusted for sidedness) = .025, standard deviation = 15 (15%), number of patients = 10, power= .0.8, difference in means = undefined, location of mean in one group as a percentile of the other group = undefined. The variable calculated was the minimum detectable difference. The probability is 80 percent that the study will detect a treatment difference at a two-sided 0.05 significance level, if the true difference between the treatments is 19.881 units or 19.8%. This is based on the assumption that the standard deviation of the response variable is 15 units or a 15% inter-individual coefficient of variation.

View: 2.19 - 2.19.6

Section 2 - Research Design and Methods

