- 3.12 **Provide a statistical justification for the total number of subjects to be enrolled into this research study at the multicenter sites or this site.*** Described below: Serial computed tomography imaging will be performed to assess the total soft tissue volume before fat grafting and afterwards at three time points: immediately post-grafting, three months post-graft and nine month post-graft. Comparisons of the post-graft tissue volume to pre-treatment volume will be performed using a paired t-test model. Repeated measures analysis of variance will be used to evaluate change over time in all outcome measures. Using standard conventions of $\alpha=0.05$ and $\beta=0.8$, an enrollment of ten patients will provide sufficient power to detect a clinically meaningful differences in the volume of soft tissue between groups.. Based on published effect sizes for clinically significant medical outcomes on the SF-36 (i.e., 0.5 to 0.7), e.g., following surgery for dentofacial deformities ($d = 0.6$) (64), and medium (0.5 – 0.79) to large (0.8 to > 3.0) effect sizes on SF-36 social functioning outcomes of neck surgery (65) and orthopedic surgery (66), it is expected that a sample of 10 patients will provide sufficient power to detect a medium effect size ($d = 0.5$) on SF-36 measures of social functioning and quality of life, applying standard conventions of $\alpha = 0.05$ and $\beta = 0.8$. Outcome of facial appearance and soft tissue volume in subjects in this protocol will be compared to those subjects in PRO09060101. Significance level (adjusted for sidedness) = .025, standard deviation = 15 (15%), number of patients = 10, power= .0.8, difference in means = undefined, location of mean in one group as a percentile of the other group = undefined. The variable calculated was the minimum detectable difference. The probability is 80 percent that the study will detect a treatment difference at a two-sided 0.05 significance level, if the true difference between the treatments is 19.881 units or 19.8%. This is based on the assumption that the standard deviation of the response variable is 15 units or a 15% inter-individual coefficient of variation.

View: 3.13 - 3.15(a)

Section 3.0 - Human Subjects

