
information. These recordings will be stored indefinitely in a secure, password protected location on the UPMC server.

5.16 If the subject withdraws from the study, describe what, if anything, will happen to the subject's research data or biological specimens.

Any identifiable research or medical information recorded for, or resulting from, your participation in this research study prior to the date that you formally withdrew your consent will continue to be used and disclosed by the investigators for the purposes described above. All research samples will be stored to include assigned code numbers, and any information linking these code numbers to the corresponding subjects' identities will be kept in a separate, secure location located in the Department of Plastic and Reconstructive Surgery at the University of Pittsburgh. Should the subject decide to withdraw or be withdrawn from study participation, the already collected samples and all digital recordings will be kept and not destroyed. We are not collecting or storing any samples for any use in future research studies with this clinical trial; samples will not be retained for testing in future studies. All samples and digital recordings collected during your participation in this clinical trial, upon your early withdraw from the study, will be kept and not destroyed, but processed specifically as outlined as stated in the research design for this trial. It is the Principal Investigator's intention to make stored samples and subject information de-identified available to secondary investigators (investigators not listed on the front page of this consent document) after all research study testing has been completed. These stored samples and associated subject information will not include subject identifiers. Subjects will be instructed that they may choose to withdraw from this study at any time, but it is important that they continue to be monitored by a physician after they receive the research Fat grafting procedure in order to ensure their safety. It is also important for the subject to contact study personnel if they later experience any side effects that they might feel are related to the research study.

5.17 Following the required data retention period, describe the procedures utilized to protect subject confidentiality. (e.g., destruction of research records; removal of identifiers; destruction of linkage code information; secured long-term retention)

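### Subjects discontinued for graft complications have no stated place in the analysis, so late volume results would probably, though not certainly, look better than in all grafted subjects

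*Combined protocol and SAP*

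**What the plan says.** Three rules take a subject out of the study:

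- Section 5.7, complications: "Development of complications that obscures evaluation of the fat graft results, i.e. severe infection at the graft site". The text adds that the infection is one that leads to further surgery.
- Section 5.7, attendance: "Noncompliance of study visits (including but not limited to completion of screening and study visit procedures". This also covers screening, before any graft exists.
- Section 5.4.2, repeated in 5.4.3 and 5.5.2: "pregnancy will result in their removal from the clinical trial".

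The statistical text is in 2.18 and, almost identically, in 3.12. Volume after grafting is compared with baseline as follows: "Comparisons of the post-graft tissue volume to pre-treatment volume will be performed using a paired t-test model". For the time course: "Repeated measures analysis of variance will be used to evaluate change over time in all outcome measures". Facial appearance and soft tissue volume are also compared with subjects of protocol PRO09060101. Neither section defines an analysis set, a method for missing visits, a replacement rule or an allowance for dropout.

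The nearest related text is 5.16, under which information recorded "prior to the date that you formally withdrew your consent will continue to be used and disclosed by the investigators". That governs use of data already in hand. It does not say how a subject without a three- or nine-month scan enters the analysis.

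**The concern.** The complication rule selects on something close to the outcome. A graft site infected badly enough to need surgery can be expected, on average, to keep less fat than an uncomplicated one. If participation ends there, the later CT volumes and quality-of-life scores are not collected, and the plan does not say what happens next. A paired t-test cannot use a subject at a visit with no scan. Conventional repeated measures ANOVA drops a subject who lacks any visit. The likely default is an analysis of uncomplicated grafts presented as the result of the procedure.

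Section 1.2 hypothesizes that "a majority of the fat tissue will remain in place over time", so the size of late retention is what readers will take from the study. With ten subjects, leaving one out can move that figure by several points. Without a rule, the choice can also be made after the data are seen.

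**Working it through.** **The plan's own figure.** Inputs from 2.18 and 3.12: SD 15, ten patients, two-sided 0.05, power 80%, detectable difference 19.881. For two groups of ten (18 df):

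15 × √(2/10) × (t₀.₉₇₅ + t₀.₈₀) = 19.876; the exact noncentral t solution is 19.874.

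Power at 19.881 is 0.800. The stated figure therefore reproduces with ten subjects in each group and no loss. That the comparator contributes ten is an inference from this match; the documents do not give its size.

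**Power after one loss.** With 9 against 10 and the same SD, power at 19.881 is 0.776 and the detectable difference is 20.49.

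**Effect on estimated retention.** Section 2.18 does not define percent retention as an endpoint, and the documents give no retention for complicated grafts, so everything here is assumed. Section 1.3 reports "retention of volume in the range of 65" percent in earlier experience. Take nine evaluable subjects with mean 65 and SD 15 (the SD used in 2.18), and one omitted graft with true retention r.

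- Nine only: 65 ± 2.306 × 15/√9 = 65 ± 11.5, so 53.5 to 76.5.
- All ten: mean = (9 × 65 + r)/10; variance = [8 × 15² + 0.9 × (65 − r)²]/9; interval = mean ± 2.262 × SD/√10.

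| r | Mean of ten | SD | 95% CI | Overstatement if omitted |
|---|---|---|---|---|
| 0% | 58.5 | 24.95 | 40.7 to 76.3 | 6.5 |
| 20% | 60.5 | 20.06 | 46.1 to 74.9 | 4.5 |
| 40% | 62.5 | 16.20 | 50.9 to 74.1 | 2.5 |
| 65% | 65.0 | 14.14 | 54.9 to 75.1 | 0 |

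If the omitted graft measured 80%, the mean of ten would be 66.5 and omission would understate retention by 1.5 points. The direction depends on complicated grafts retaining less than the rest.

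**Test against pre-graft volume.** Letting percent retained stand in for volume gain, the worst case (r = 0) gives t = 58.5/(24.95/√10) = 7.41, p = 0.00004. The conclusion that volume rose is unaffected.

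**The case against.** The strongest reply is that no planned analysis changes its answer. The paired test is safe, power barely moves, and the retention figures concern an endpoint that 2.18 does not define. The plan analyses total soft tissue volume, and section 3.13 allows grafts of 5 to 150 cc, so an unweighted percentage-point shift does not carry over directly. All of that stands, and it limits the size of the point.

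A second reply is that the trigger is obscured evaluation, not graft failure. After infection and further surgery, CT volume may misstate retained fat in either direction. Reporting evaluable grafts, with complications listed separately, is then a defensible choice. This also stands in part, but the choice has to be written down, and the plan does not do so.

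Third, repeated measures ANOVA does not by name require dropping incomplete subjects, and 5.13 provides for monthly review of retention and adverse events. The first shows that the text is open rather than wrong. The second is oversight, not an analysis rule.

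A reader might go further and infer that one complicated graft decides whether the data support a majority remaining. The documents do not support that. No test or interval against 50% is planned, and the mean stays above 50% in every case shown. The interval reaches below 50% only at the assumed 0% and 20%.

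**Conclusion.** The gap is real and of moderate weight. A discontinuation rule related to the outcome is paired with methods that, as usually run, omit subjects without later scans, and no analysis set or missing-data rule says otherwise. Late volume results would probably look better than in all grafted subjects. On the assumed values, one omitted graft overstates mean retention by 0 to 6.5 points.

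The probable direction rests on one assumption that the documents make plausible but do not quantify: that complicated grafts retain less. For missed visits and pregnancy the direction is unknown, and failures at screening do not concern grafted subjects at all. It is tempting to attach a probability to losing a graft this way, but the documents give no rate for complications of this severity, so none should be quoted. Nor do the documents support saying that the baseline comparison is in danger or that the comparison with PRO09060101 becomes underpowered.

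**What to change.** In 2.18 and 3.12:

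1. Define the analysis set as all grafted subjects. This also disposes of failures at screening.
2. Replace repeated measures ANOVA with a linear mixed model (visit fixed, subject random, small-sample degrees of freedom such as Kenward-Roger) that uses every available visit.
3. Because that model does not by itself correct loss related to the unseen outcome, add a prespecified sensitivity analysis. It would assign grafts lost to a complication a range of values, from low to the mean of the other subjects, labelled as assumptions.
4. Report discontinuations by reason beside the evaluable-only result.
5. Apply the same rule to the PRO09060101 data where they allow it.

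No change to 5.7 is proposed. Follow-up and imaging safety for discontinued subjects stay with the investigators.

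The cost is a few sentences, a standard model and one extra table. The sensitivity interval will be wider: with one graft at 0% the SD rises from 15 to about 25, which is why that case belongs in a sensitivity analysis and not in the main one.
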